## D6. Study Procedures

Research staff will approach potentially eligible participants during inpatient hospitalization in either the medical unit or the psychiatric inpatient unit. If interested, informed consent will be obtained and research staff will coordinate with the Veteran patient and inpatient staff in order to conduct the baseline assessment. Eligible patients will be enrolled in the study.

After enrollment patients will be randomized to 1) Safety Assessment and Follow-up Evaluation (SAFE) or 2) CLASP for a six month period. We will use the urn randomization strategy described by Wei [63] and Stout [64] to help insure balance among treatment groups. Urn randomization is a stratified randomization technique, which randomly assigns patients of a given subgroup to treatment conditions, but systematically biases the randomization in favor of balance among the treatment conditions on the stratification variables. For this study, we will be balancing the treatment groups on the following stratification variables: 1) gender of participant (male or female); 2) number of previous suicide attempts (zero, one, many) and 3) recent intake for suicidal ideation vs suicide attempt. We have successfully used the urn randomization procedure in several previous treatment outcome studies [65, 66] and have acquired an electronic file that contains the algorithm for urn randomization

[67]. This file also will provide the ability to monitor effectiveness of our stratification and randomization procedures. Patients assigned to the CLASP intervention will be asked to identify and reach out to a significant other to participate with them. For those in the CLASP intervention, research staff will attempt to complete 3 in-person individual sessions and 1 in-person joint session while the patient is hospitalized. In the event that the patient is discharged prior to the completion of in-person sessions, those sessions will be scheduled in the 1-2 weeks after the patient has left the hospital and will be conducted in assessment rooms in the Research building.

#### **D6.1 Treatments.**

- 1) *Description of CLASP.* CLASP differs from typical psychotherapy in that it involves a relatively unique combination of case management, with the implementation of both individual and family-based therapeutic strategies. The CLASP provider's primary role is in monitoring suicide risk areas, and if problems occur in these areas, to help facilitate the patient and significant other in resolving these difficulties. Thus, the CLASP provider's role is more of a treatment "advisor" than "therapist." For example, the CLASP provider would not attempt to provide psychotherapy to address increased depression, but would instead function more as an advisor, by exploring potential treatment options for depression with the patient and significant other. While the CLASP provider does provide some family and individual strategies, these types of interventions are: a) used sparingly, b) not the major focus of the CLASP telephone calls, and c) are done in the context of a more "facilitator or case manager" type relationship. For these reasons and in order to emphasize the difference between the CLASP provider and the patient's VA providers, the CLASP provider identifies him/herself to the patient as a "CLASP Treatment Advisor." Furthermore, the CLASP advisor is more proactive than typical clinicians. The CLASP advisor initiates the telephone calls to patient and significant other, and will continue to contact each as necessary, whereas typically, clinician attempts to contact patients may be limited, except in some specific types of treatment (e.g. DBT). Furthermore, unlike most outpatient treatments, CLASP involves both patient and significant other, providing consultation to both.
  - a. *Individual In-Person Meetings.* Meeting 1 focuses on rapport building. The advisor inquires about the events leading to hospitalization, emphasizing the links between identified risk factors and suicidality. The advisor assesses current risk behaviors. The advisor also provides brief psychoeducation about suicidality. Next, values clarification is introduced based on ACT to motivate change and instill hopefulness. In Meeting 2, the advisor reviews and finishes the values clarification discussion as needed and helps the patient define specific behavioral goals that are consistent with the values. The advisor helps the patient define a list of short-term, values-consistent goals. The majority of Meeting 3 is spent formulating an individualized "Life Plan." The Life Plan document contains various questions for the patient and advisor to discuss and record responses, such as "What is my plan of action for keeping safe?" and "How will I recognize my early warning signs so I can take action sooner?" The advisor and patient also formulate a specific safety plan to address any suicidality following hospitalization. Potential barriers to attending scheduled sessions within the VA post-discharge are discussed and the role of the Suicide Prevention Coordinator is discussed.
  - b. *SO In-Person Meeting.* Meeting 4 includes the advisor, patient, and a significant other (SO) following the FITT format. The advisor reviews the psycho-educational information with the patient and SO. The advisor asks the SO to discuss his/her perspective on the patient's recent hospitalization. The majority of the session is spent reviewing the patient's Life Plan. The advisor facilitates a discussion between the SO and patient about the role the SO can play in the treatment plan to support the patient's goals. If severe patient-SO conflict is identified referrals for family therapy are provided.
  - c. *Telephone contacts.* Following the in-person meetings, the advisor conducts Telephone Contacts 1-11 with the patient and their SO individually. To further personalize the intervention and decrease potential treatment burden, each session is 15-30 min in length based on the number and severity of clinical issues identified. Sessions are conducted on a schedule of decreasing frequency for a target of 11 sessions over 6 months. At the start of

each contact, the advisor conducts a quick assessment of risk factors (e.g., psychiatric severity, suicidality, treatment adherence, social support) since last contact. If suicidality is identified, this is discussed first and a safety plan is developed. The advisor facilitates problem-solving and communication between the patient and SO. The advisor discusses problems in terms of values strategies and in reference to the previously developed Life Plan document. If a problem develops that cannot be solved in this manner, the advisor may obtain permission to contact the patient's primary treatment provider directly or temporarily increase the frequency of the phone contacts during times of crisis. The SO phone contact proceeds in a similar manner. The VA Suicide Prevention Coordinator will be informed of any increase in risk.

2) *Description of Control Condition.* The choice of a comparison or control condition for suicide prevention research has been the subject of much debate [68]. For a variety of ethical, pragmatic and research concerns, the most commonly used control group has been some variant of "Treatment as Usual (TAU)." Although use of TAU as a control group has some limitations [69], it also has many advantages [70]. Since the CLASP intervention is designed to be an "adjunctive" intervention, the use of a variant of TAU seems particularly appropriate. Empirically, this decision allows for the evaluation of CLASP as a true adjunctive intervention, as we will be able to evaluate the additive benefits of CLASP over and above TAU. This design also reflects the manner in which CLASP would likely be implemented in the VA setting (i.e., to Veterans already identified as being at risk for suicide). However, given the high risk nature of this proposed sample, in order to provide an ethically appropriate "comparison" condition, we have developed and piloted a comparison condition which enhances "treatment as usual" with additional assessment and clinician feedback.

a. The SAFE condition consists of clinical treatment as typically provided. Participation does not influence the patient's ongoing clinical care. However, in addition to treatment as usual, patients participating in SAFE receive enhanced assessment and monitoring services. The enhanced monitoring consists of regular assessments of suicidal ideation and risk factors on admission to the hospital, discharge, and follow-up assessments. We obtain releases to share information with the patient's clinician(s). At the baseline, 3, and 6 month assessment times, we provide the patient's clinician(s) with a standardized report based on these assessments that summarizes the patient's level of suicidal ideation and identified risk factors.

**D6.2 Advisor Supervision.** CLASP advisors will receive ongoing weekly supervision in a group format. Additionally, sessions are recorded for supervision purposes and regularly reviewed to prevent protocol "drift" throughout the study. Remedial training and practice is provided to advisors who do not maintain acceptable adherence and competency. Yearly "refresher" workshops are provided to advisors throughout the study to ensure continued adherence to the protocol

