### **F3.1 Operationalization of Outcomes.**

#### 1) Primary Outcome

- a. *Suicide Attempts*. The number of patients who make a subsequent suicide attempt and total number of attempts will be assessed using 12 month data collected from all possible sources, including follow-up assessments (C-SSRS), b) hospital chart reviews, c) significant other reports, and d) community clinician reports.

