If our staff identify an individual with significant clinical deterioration or who report any suicidal ideation with plan or intent they will contact [name] who will evaluate the patient over the phone or in person. [name] will generate a list of mental health services in case of emergency. In the event that a study participant reports significant deterioration but is not in immediate danger of hurting himself, we will take the following actions. First, we will inform the patient about the procedures for contacting emergency services should they find themselves at risk for self-harm. Second, for individuals stable on medications, we will request permission to contact their outpatient psychiatrist to inform them of their deterioration. Finally, the participant will be provided with additional mental health referrals. In the event that a participant is acutely suicidal, the research staff member will walk the Veteran over to interim care or the ER for immediate safety assessment. All adverse events will be immediately recorded and reported to the Providence VA Hospital IRB.

- 5) The potential for adverse events during the study will be minimized by the following procedures:
- Since the intervention being evaluated in this study is an adjunctive intervention, participation in the study will not prohibit involvement in any other type of treatment. All subjects will be allowed (and/or encouraged) to participate in whatever type or amount of treatment is thought to be clinically indicated for the patient. Thus, participation in the study will not cause any subject to be deprived of a clinically appropriate treatment.
  - All subjects in the study will receive enhanced monitoring of their clinical condition. As part of the SAFE intervention, we will obtain release of information forms and will routinely communicate the results of this monitoring to the patient's clinician(s). Further, patients will be informed that notes will be entered into CPRS and thus will be available to their VA treatment providers. CLASP advisors will routinely monitor levels of suicidal ideation and risk, as well as overall psychiatric symptoms, and take appropriate clinical action when necessary to reduce risk.

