  - We will have procedures in place to respond to increased levels of suicide risk if reported. Briefly, if any patient manifests significant psychiatric symptomatology during study assessments, we will either: a) inform the patient's clinician and/or primary care physician, or b) if the patient is not currently in treatment, we will provide the patient with a referral to a qualified clinician and will contact the Providence Suicide Prevention Coordinator. In the event that a subject manifests significant suicidal or homicidal ideation or risk, we will take whatever steps necessary to insure the patient's and/or others' safety. Depending upon the specific situation, these steps may involve: a) escorting the patient to the hospital's admitting office for an emergency evaluation, b) alerting inpatient staff to the patient's level of risk, c) notifying patient's clinician, primary care physician, and/or family member or d) calling the appropriate police departments.
- 6) All serious adverse events will be immediately recorded and reported to the Providence VAMC IRB.

**G2.3 Procedures for Handling Suicidality.** Regarding imminent self- or other-harm, there is a specific protocol within the Providence VA Medical Center System for handling behavioral crises, which is contingent upon whether the person(s) is on-site or off-site when such emergencies arise. On site, we have "Team 3" buttons for each clinician or research assistant that are directly linked to the Providence VA Medical Center police department and additionally request a team of mental health workers trained in crisis management. If during the course of the assessment the participant reports suicidal ideation, the research assistant will immediately contact a study clinician. If the participants experience any crises between therapy or assessment sessions, they will be instructed to immediately

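### Suicide attempts can be ascertained differently by arm: scheduled clinician contact is written only into SAFE, significant-other and advisor contact only into CLASP, and F3.1 sets no common collection rule

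*Combined protocol and SAP*

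**What the plan says.** **Clinician contact in SAFE.** D6.1, in the description of the control condition, says "We obtain releases to share information with the" patient's clinicians. It continues: "At the baseline, 3, and 6 month assessment times, we provide the patient's clinician(s) with a standardized report". G2.2 item 5 repeats the link to that arm: "As part of the SAFE intervention, we will obtain release of information forms and will routinely communicate the results of this monitoring" to the clinicians. No scheduled report is described at 9 or 12 months.

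**Clinician contact in CLASP.** Under telephone contacts, D6.1 says that when a problem cannot be solved on the calls, "the advisor may obtain permission to contact the patient's primary treatment provider directly".

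**Clinician contact in either arm.** G2.2 item 5 also provides that "if any patient manifests significant psychiatric symptomatology during study assessments, we will either: a) inform the patient's clinician and/or primary care physician". This is triggered by an event and is not a routine inquiry.

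**Contacts that exist only in CLASP.** D2 and D2.3 enrol significant others only for Veterans assigned to CLASP. D6.1 sets a target of 11 telephone contacts over 6 months, held separately with the patient and the significant other, each starting with a risk check that includes suicidality.

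**Outcome sources.** F3.1 builds the 12-month primary outcome from the C-SSRS assessments, hospital charts, "c) significant other reports, and d) community clinician reports". It does not restrict any source by arm or say how each is to be collected. Re-hospitalization in F3.1 also draws on clinicians' reports, beside the Treatment History Interview and hospital records.

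**Blinding.** D5 has follow-up assessments done by an evaluator who does not know the assignment. Nothing comparable is stated for reports arriving from clinicians, significant others or advisors.

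**The concern.** The comparison of attempt proportions is fair only if an attempt is equally likely to be found in either arm. The blind C-SSRS interviews and hospital chart review apply to both arms. The other two named sources are tied to contacts that belong to one arm's treatment package.

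The events at risk are attempts treated outside the VA and not disclosed at an assessment. In SAFE, such an attempt could surface because the clinician holds a release and hears from the study on schedule. In CLASP, it could surface because a significant other or the patient tells the advisor. Each route can shift the observed odds ratio when the true effect is nil, and can distort its size when the effect is real. Re-hospitalization is exposed in the same way. No later analysis can recover attempts that were never seen, so the matter has to be settled at enrolment.

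**Working it through.** **Inputs**
- SAFE risk p = 10/47 = 21.3% and CLASP risk 3/39 = 7.7% (F5, pilot).
- One-tailed alpha .05, Fisher's exact test, N = 200, stated power .82 (F5).
- 100 per arm: the allocation ratio is not stated; this is inferred from the 100 significant others planned for CLASP (D2).
- u: share of attempters known only through a community clinician and missed in CLASP. v: share known only through significant others or advisor calls and missed in SAFE. The documents give neither, so both are assumed over 0 to 20%.

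**Step 1: the plan's own figure.** Summing binomial probabilities over all outcomes that the one-tailed Fisher test rejects, with 100 per arm, gives power .833 at 3/39 v 10/47 and .799 at the rounded 8% v 21%. The stated .82 is reproduced closely enough. It does not depend on this point.

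**Step 2: no true effect, unequal ascertainment.** Observed risks are p(1 − u) in CLASP and p(1 − v) in SAFE. The observed odds ratio is

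OR = [p(1 − u) / (1 − p(1 − u))] ÷ [p(1 − v) / (1 − p(1 − v))].

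For u = 10%, v = 0: CLASP risk 0.2128 × 0.9 = 0.1915; OR = (0.1915/0.8085) ÷ (0.2128/0.7872) = 0.876.

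Cells show the odds ratio and the one-tailed Fisher rejection rate in favour of CLASP:

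| u \ v | 0 | 5% | 10% | 20% |
|---|---|---|---|---|
| 0 | 1.000; 3.6% | 1.067; 2.3% | 1.141; 1.4% | 1.318; 0.5% |
| 5% | 0.937; 5.2% | 1.000; 3.5% | 1.070; 2.3% | 1.235; 0.8% |
| 10% | 0.876; 7.5% | 0.935; 5.2% | 1.000; 3.5% | 1.155; 1.4% |
| 20% | 0.759; 14.6% | 0.810; 10.8% | 0.866; 7.6% | 1.000; 3.4% |

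The first column is the clinician source alone, fully open in SAFE and fully closed in CLASP. The first row is the CLASP-only sources alone. Equal shares cancel and unequal shares do not.

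**Step 3: pilot effect real.** Applying u and v to 7.7% v 21.3%, power moves from .833 to .880 (u = 10%, v = 0), .721 (u = 0, v = 10%) or .575 (u = 0, v = 20%). An asymmetry against CLASP is therefore costly too.

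**The case against.** The strongest reply is that the SAFE channel runs outward. Its releases are for sharing information with clinicians, and its reports go to them. No section describes clinicians being asked about attempts, in either arm, and the reports stop at 6 months of a 12-month outcome. This stands. That more attempts would come back through clinicians in SAFE is an inference: clinicians under release and in regular contact are likelier to report. If the inference fails, F3.1 names a source with no described method of collection, and the remedy is the same.

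It can also be said that CLASP patients may have releases as well. The G2.2 bullet opens with "All subjects in the study will receive enhanced monitoring of their clinical condition" before it attributes the releases to SAFE, and symptom-triggered contact covers any patient. C1.2 reports 149 community providers contacted in the pilot, about 1.7 per patient if spread over all 86 and 3.2 if over the 47 in SAFE, which does not settle the question. These points make the text ambiguous. They do not supply a common rule.

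Third, an attempt known only from a clinician must escape four blind assessments and hospital record review, so large shares may be unrealistic. Nothing in the documents supports 20% in particular, and a source only partly closed in CLASP gives a smaller shift. Step 2 also uses the sample-size test; F3.2 plans a covariate-adjusted odds ratio with a robust interval, for which the unadjusted odds ratios above are only a guide.

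Finally, a reader might infer that the plan as a whole is biased in favour of CLASP. The documents do not support that. Significant-other reports and advisor calls exist only in CLASP and raise detection there. Nor is it clear how much they add: D2 and G2.2 say that significant others complete no questionnaires or interviews, so how their reports reach the outcome is not described.

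**Conclusion.** The concern holds as one of arm-dependent ascertainment of unknown net direction. Followed as written, the plan lets unblinded reports from sources attached to one arm's treatment decide whether a patient counts as having attempted suicide.

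The clinician source alone would tend to favour CLASP, by an odds ratio of 0.94 to 0.76 over assumed shares of 5% to 20%. This rests on no true effect, 21.3% risk, 100 per arm, and a source fully closed in CLASP and fully open in SAFE, so it is a worst case for that one channel. The CLASP-only sources alone give 1.07 to 1.32 over the same range. Together the result may be null or go either way: 10% against 10% gives 1.00, 10% clinician-only against 20% significant-other or advisor-only gives 1.16, and the reverse gives 0.87.

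Two stronger statements should not be made: that the trial is biased toward CLASP overall, and that SAFE already has a clinician query for attempts that CLASP lacks. Possible cancellation is no defence, since nothing in the design makes the two shares equal. The plan should be changed because the change is cheap and must be made prospectively.

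**What to change.** 1. **D4/D6:** at baseline, before randomization, seek the same clinician release from every Veteran, covering information sent and received. Refusals then cannot depend on assignment.
2. **F3.1:** define the primary attempt outcome and the re-hospitalization outcome from sources collected identically in both arms: the blind C-SSRS and Treatment History Interview, and hospital and death-record review. Clinician reports join this list only if clinicians in both arms are queried with the same form at the same months, through month 12.
3. **F3.1/F3.2:** attempts or admissions known only from significant others, advisor calls, or clinician reports outside the common query enter a sensitivity analysis only.
4. The SAFE feedback reports stay as they are.

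**Cost:** one release form for all participants and a few sentences in F3.1 and F3.2. If a clinician query is used, staff time is needed in both arms, because it would be new in both. The primary analysis may lose a few events, with some loss of power; the sensitivity analysis will show how many.

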## **E. Early Termination**

If participants decide to withdraw from the program we will ask their permission to contact them for the assessment. We will provide additional referrals as needed or as requested if the participant decides to withdraw from the study.

## **F. Data Analysis**

### **F1. General Approach**

Analyses will be conducted using a combination of R [71] SPSS, and MPlus 6.12 [72]. Data initially will be examined for assumptions and appropriate estimation procedures will be applied as a function of data characteristics. As appropriate, maximum likelihood estimation with robust standard errors (MLR) will be applied, permitting analysis of data missing at random and non-normal distributions. Interpretation of results will be adjusted to account for number of tests performed using the step-down procedure of Benjamini and colleagues [73, 74]. Latent and longitudinal modeling (i.e. growth curve modeling) will be adopted wherever possible to permit simultaneous estimation procedures, maximize power, and allow comprehensive theoretically-informed tests of the aims.

